3.3.2 Follow-up for withdrawn subjects

Describe when and how to withdraw subjects from the study; the type and timing of the data to be collected for withdrawal of subjects; whether and how subjects are to be replaced; the follow-up for subjects withdrawn from investigational treatment.

If a participant (parent or provider) decides to stop before the study's conclusion, a member of the research team will ask if they wish to have their information used at all; if no, we will purge their information from our database. If the participant indicates that we can use their unidentifiable information, we will retain their available survey data and remove their identifiers from the master list.

4.0 Recruitment Methods

4.1 Identification of subjects

Describe the methods that will be used to identify potential subjects or the source of the subjects. If not recruiting subjects directly (e.g., database query for eligible records or samples) state what will be queried, how and by whom.

StudyFinder: If you intend to use StudyFinder (<http://studyfinder.psu.edu>) for recruitment purposes, please indicate this in section 4.1 along with any other methods for identifying subjects. Note that information provided in this protocol should be consistent with information provided on the StudyFinder page in your CATS IRB study.

For Penn State Hershey submissions using Enterprise Information Management (EIM) for recruitment, attach your EIM Design Specification form on the Basic Information page in CATS IRB (<http://irb.psu.edu>). See HRP-103 Investigator Manual, "What is appropriate for study recruitment?" for additional information.

We will utilize our relationship with community partners (i.e., providers of the parent-education programs) and Children and Youth agencies to recruit provider agencies.

After obtaining provider buy-in at both experimental and control sites, we will recruit participants directly through providers at these agencies.

For experimental sites, that is those who are randomized to add the CSA module onto the existing PE program, providers will be recruited to participate in the fidelity research at the time of training in SPSHK.

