3.3 Early Withdrawal of Subjects

3.3.1 Criteria for removal from study

Insert subject withdrawal criteria (e.g., safety reasons, failure of subject to adhere to protocol requirements, subject consent withdrawal, disease progression, etc.).

1. Participant decides to withdraw from the parent-training program
2. Participant decides to withdraw at any point from the survey

Providers who decide to not deliver the module.

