7.0 Study Design and Procedures

7.1 Study Design

Describe and explain the study design.

This research will utilize a randomized controlled trial (RCT) design. As this research includes three parenting programs, Incredible Years, PAT, and SafeCare, three RCTs will be conducted simultaneously. Randomization will occur at the site level to reduce the potential for contamination; as such, recruited parents will not be informed of the randomization process. When sites agree to participate (i.e., be randomized) they agree to implement the evidence-based parenting program plus the added module as they would typically implement the parenting program. Although the module is not evidence-based, they are agreeing to deliver as if it were standard procedure.

This section describes the design and procedures for the three RCTs: (1) *Incredible Years RCT*; (2) *Parents as Teachers RCT* and (3) *SafeCare RCT*. However, there are commonalities between the three trials:

- There will be two groups of providers— one assigned to deliver the parenting program and one assigned to deliver the parenting program plus additional SPSHK module at the end of the last session (described below), in support of the research question.
- Parents in the control group will complete assessments at four time points: pre-parenting intervention, post-parenting intervention, one-week post parenting, and one month post-intervention.
- Parents in the experimental group will complete assessments at four time points: pre-parenting intervention, post-parenting intervention, post-module, and one month post-intervention.
- For the experimental group, fidelity monitoring procedures will also occur in sessions for each enrolled provider-subjects. Parents and provider-subjects of these sessions will each complete a fidelity assessment instrument. With the parent’s permission, the provider will audio record two experimental sessions.

Different measures will be asked at specific assessment periods:

Measure Name (file name in supporting documents attachments)	Construct	Timing of Delivery (by Protocol Section description paragraph)
Alabama Parenting Questionnaire (APQ; ‘Measure_APQ.docx’)	Parenting behaviors and responding to child’s externalizing behaviors: subscales of Parental Involvement, Positive Parenting, Inconsistent Discipline Practices	7.2.1, 7.2.3, 7.2.5, 7.2.6

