7.2.1 Pre-parenting Intervention Assessment

Provide a description as defined above and format accordingly.

As described above, parents are recruited to participation in the research after independently signing up to participate in Incredible Years, Parents as Teachers, or SafeCare, and the agency/site providing their parenting program would have already agreed to randomization (and experimental condition providers received their training in the SPSHK module). Following consent and before any intervention has occurred, the parents will be given a paper copy of the assessment. A member of the research team will distribute surveys (identified only by a unique code—see Section 9) at the beginning of the first session to parents who have consented to participate.

The assessment is given in a booklet format. At this assessment point, parent survey booklets include the APQ, AUDIT, CES-D, DAST, ISEL-SF, READI-SF, a demographics questionnaire, and the module assessment of parents’ attitudes, knowledge, and behaviors of CSA prevention (measures described above in Section 7.1). Providers in the group sessions (Incredible Years) will engage with parents who do not wish to participate separately at this time.

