17.0 Other Approvals

17.1 Other Approvals from External Entities

Describe any approvals that will be obtained prior to commencing the research (e.g., from cooperating institutions, community leaders, schools, external sites, funding agencies).

Agencies that implement Incredible Years or PAT or SafeCare parent-training programs will be approached by mail, email, and/or phone call and invited to participate in the study. Presentations or webinars will be made available to provide more information should agencies desire. Facilitators (i.e., the individuals who actually implement the programs with parents) will then be recruited and then randomized to either (a) business-as-usual implementation of their respective program or (b) implementation of their respective program and the additional, one-session CSA module. As we recruit sites to participate we will ask about their required approvals. At this time, no site that has agreed to participate has an external approval process. All they require is a letter from the PSU IRB saying this research is approved.

As a site is recruited, a document agreement will be acquired from someone in an oversight position who has a decision-making capacity over potential subjects.

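### Sections 4.1, 7.1 and 17.1 do not agree on whether facilitators commit before or after allocation, or on which unit is randomized, which leaves room for provider selection in the experimental arm only

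*Combined protocol and SAP*

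**What the plan says.** Section 4.1 describes recruitment in two steps: "After obtaining provider buy-in at both experimental and control sites, we will recruit participants directly through providers at these agencies". It then explains which sites it means: "For experimental sites, that is those who are randomized to add the CSA module onto the existing PE program".

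Section 17.1 describes the facilitators, the people who deliver the programs to parents, in a different order. After agencies are invited, facilitators "will then be recruited and then randomized to either (a) business-as-usual implementation of their respective program" or to the program with the added session.

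Section 7.1 names a different unit: "Randomization will occur at the site level to reduce the potential for contamination". It also describes an advance commitment, made by the site: "When sites agree to participate (i.e., be randomized) they agree to implement the evidence-based parenting program plus the added module". Section 7.2.1 says that when parents are approached the agency or site "would have already agreed to randomization (and experimental condition providers received their training in the SPSHK module".

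Section 3.3.1 includes among its removal criteria "Providers who decide to not deliver the module". No section says what becomes of the parents served by such a provider.

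**The concern.** Randomizing sites balances the facilitators and families present at the moment of allocation. It does not balance a subset of facilitators who opt in after learning their arm. Only the experimental arm adds a training day, an extra session on sexual abuse and fidelity forms, so only that arm offers something to decline.

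Parents are reached through providers (4.1), and providers already know which families are eligible before any approach (4.4). A facilitator who declines early could therefore take a whole caseload, or an Incredible Years group of about 10, out of one arm. If willing facilitators differ in skill, in comfort with the topic or in the families they serve, the arms would differ for reasons other than the module. This is separate from parents' own consent and would remain even if parent recruitment were blind to allocation.

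**Working it through.** The plan gives no figure for this point: no number of sites or facilitators, no refusal rate and no between-provider variance. The check is therefore mainly a comparison of sections.

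**Order of facilitator agreement and allocation**
- 4.1: buy-in comes before parent recruitment and is located at sites named by arm, the experimental ones being those that have been randomized. It does not state whether buy-in comes before or after randomization.
- 17.1: facilitators are recruited first and randomized second.
- 7.1 and 7.2.1: agreement precedes randomization, but it is given by the site or agency. Neither section records the individual facilitator's agreement.

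**Unit of randomization**
- 7.1 and 4.1: the site.
- 17.1: the facilitator.

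Staff working from 4.1 and staff working from 17.1 could run the trial differently.

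**What happens after a refusal**
- 3.3.1 allows for a provider who chooses not to deliver the module. Control providers have no module to deliver, so the event exists in one arm only.
- No section states whether that provider's families are still approached, retained or analysed. Section 8.3 fixes no analysis population and leaves the model to depend on recruitment and participating sites.

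**Illustration of scale, on assumed inputs.** Let q be the share of experimental families lost through declining facilitators, and d the amount by which those families would score below the rest, in SD. Neither is in the documents. Assume q = .10 to .30 and d = .3 to .5.
- Shift in the arm difference with no module effect: b = q × d, from .10 × .3 = .03 to .30 × .5 = .15 SD. Against the planned effect of .45 this is .03/.45 = 7% to .15/.45 = 33%.
- Standard error implied by 80% power at .45 (8.2): .45/(1.960 + .842) = .1606.
- Two-sided rejection rate under the null: Φ(b/.1606 − 1.96) + Φ(−b/.1606 − 1.96), which is 5.4% at b = .03 and 15.4% at b = .15, with no baseline adjustment.
- With baseline adjustment, taking the .7 autocorrelation in 8.2 (given there for Incredible Years) as the pre-post correlation, the remaining shift is (1 − .7) × b = .009 to .045 SD. At the same standard error the rejection rate is 5.0% to 5.9%.

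If declining facilitators serve higher-scoring families, d changes sign and the bias runs the other way.

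**The case against.** The strongest reply is that 4.1 never says buy-in follows allocation. It orders buy-in only against parent recruitment, and naming sites by arm may be description after the fact. The one explicit statement about facilitators, in 17.1, gives the order one would want, and 7.1 has sites commit to the module in advance. The word provider may also mean the agency: the sentence before the quoted one in 4.1 speaks of recruiting provider agencies. On that reading buy-in is simply the site agreement of 7.1. All of this stands, and it is why the point is one of ambiguity.

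The removal rule in 3.3.1 is also weaker evidence than it looks. It governs enrolled provider-subjects, who belong to the fidelity research. Experimental providers are trained before parents are approached (7.2.1), and the module comes weeks later. A provider who withdraws then leaves enrolled parents without the module, which is non-delivery and not selection before approach. This stands too. It leaves open how such parents are analysed.

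Finally, both arms complete demographics, the parenting and depression scales, the readiness scale and the primary Module Assessment before any intervention (7.2.1), so a difference between families would show at baseline. That is right for family differences. It does not cover a difference in facilitator skill that affects later change, and 8.3 permits plain t-tests, so baseline adjustment is not assured.

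A reader might infer that the arms' parents do come from differently selected providers, or that the false-positive rate is about 15%. The documents support neither. The first treats one reading of 4.1 as settled against 17.1. The second is the extreme corner of assumed inputs in an unadjusted comparison.

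**Conclusion.** The sections conflict on a step that bears on selection bias. Section 4.1 reads as buy-in at allocated sites, 17.1 says the opposite for facilitators, 7.1 and 7.2.1 secure only the site's or agency's agreement, and 7.1 and 17.1 disagree on the unit. The concern becomes a bias only if 4.1 is followed and provider means the individual facilitator. In that case declining is possible in one arm only, and the plan is silent on the families affected. Size and direction cannot be derived from the documents. On the assumed inputs the effect ranges from negligible to material, depending largely on whether baseline is adjusted for. Confidence is low. The correction is still worth making, because it costs little if the sponsor already intends the 17.1 order and removes an avoidable source of bias if not.

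**What to change.** Reconcile 4.1, 7.1 and 17.1 so that they state one order and one randomized unit, the site. Before a site's allocation is disclosed, list every facilitator of the program there and record each one's agreement to deliver either condition. Recruit parents from all listed facilitators in both arms. State in 8.3 that parents are analysed in the arm to which their site was randomized, whether or not the module was delivered. Report by arm the number of facilitators listed, the number who later declined, and their eligible families.

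The cost is a wording change, a short facilitator log per site, and an allocation that waits for facilitators' answers. A few facilitators may decline at that earlier point, but they would do so without knowing their arm.

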4.2 Recruitment process

Describe how, where and when potential subjects will be recruited (e.g., approaching or providing information to potential subjects for participation in this research study).

Providers at the experimental groups who are trained to deliver SPSHK will be presented with the opportunity to participate in the fidelity research at the time of training. The trainers will read the attached recruitment script and obtain consent.

Parents who have enrolled in Incredible Years or PAT or SC will be recruited by a member of the research team at the first session of their respective parenting program; that is, before any intervention is delivered. A parent's participation in research (i.e., the surveys) does not affect their ability to participate in the original parenting program (i.e., Incredible Years or Parents as Teachers or SafeCare).

4.3 Recruitment materials

List the materials that will be used to recruit subjects. Add recruitment documents to your study in CATS IRB (<http://irb.psu.edu>) on the "Consent Forms and Recruitment Materials" page. For advertisements, upload the final copy of printed advertisements. When advertisements are taped for broadcast, attach the final audio/video tape. You may submit the wording of the advertisement prior to taping to preclude re-taping because of inappropriate wording, provided the IRB reviews the final audio/video tape.

StudyFinder: If you intend to use StudyFinder (<http://studyfinder.psu.edu>) for recruitment purposes, you do not need to upload a separate recruitment document for information placed on the StudyFinder site to your study in CATS IRB. Necessary information will be captured on the StudyFinder page in your CATS IRB study.

Attached is the verbal recruitment script for providers in the SPSHK training to participate in the fidelity research.

Attached to this application is the script for recruitment of parents who have signed up for Incredible Years or PAT or SC but have not yet begun sessions. Separate recruitment scripts are included for control and treatment groups.

For parents who will be asked to be recorded, a separate half-page flyer is available for the provider to use to explain why the recording is happening; the provider may choose to use this at his/her discretion.

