4.4 Eligibility/screening of subjects

If potential subjects will be asked eligibility questions before obtaining informed consent, describe the process. Add the script documents and a list of the eligibility questions that will be used to your study in CATS IRB (<http://irb.psu.edu>) on the "Consent Forms and Recruitment Materials" page.

StudyFinder: If you intend to use StudyFinder (<http://studyfinder.psu.edu>) for recruitment purposes, any scripts (phone, email, or other) used when contacting StudyFinder participants as well as any eligibility screening questions must be added to your study in CATS IRB (<http://irb.psu.edu>) on the "Consent Forms and Recruitment Materials" page.

There are no additional screening questions for providers.

We will not be asking subjects additional eligibility questions. As they are recruited by providers, we are using the eligibility criteria of the parenting program (Incredible Years or PAT or SC) as the only screener.

In other words, if they are enrolled or enrolling in either of these programs, and meet the other criteria (English-speaking, over 18, and a parent/caregiver to a child under 13) then there are no additional screening items. These eligibility criteria (and whether a parent meets them or not) will be known by the providers prior to approaching a family. If a parent receiving PAT or SC is ineligible, they will not be presented with an opportunity to participate. Incredible Years providers will conduct sessions with eligible parents for the research and separate sessions for ineligible parents.

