16.5 Process for informing Study Team

Describe the training plans to ensure members of the research team are informed about the protocol and their duties, if applicable.

Study Team members housed at Penn State have extensive training in the protection of human subjects and appropriate, ethical research. The team holds regular meetings to discuss the implementation and research protocols, survey instruments, and their specific duties.

The PSU research team members will provide a training day for all providers who will implement the module and consent participants. The implementation and research protocols will be explained, reviewed, and modeled. Each person who will obtain consent and explain procedures will practice in a role-play format supervised by the PI prior to entering the field.

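### Parents are recruited after their site is allocated, with separate scripts by arm and an unsettled recruiter role, so consent could differ by arm in a way that site randomisation cannot remove

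*Combined protocol and SAP*

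**What the plan says.** Section 7.1 sets the unit of allocation: "Randomization will occur at the site level to reduce the potential for contamination; as such, recruited parents will not be informed of the randomization process". Section 7.2.1 sets the order of events. When a parent is recruited, the agency "would have already agreed to randomization (and experimental condition providers received their training in the SPSHK module". Section 17.1 has facilitators randomised rather than sites, but on either account allocation precedes the approach to parents.

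Section 4.3, on parent recruitment, says "Separate recruitment scripts are included for control and treatment groups".

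On who recruits, the sections differ:

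- Section 4.1: "After obtaining provider buy-in at both experimental and control sites, we will recruit participants directly through providers at these agencies".
- Section 4.2: parents "will be recruited by a member of the research team at the first session of their respective parenting program".
- Section 4.4: "As they are recruited by providers, we are using the eligibility criteria of the parenting program". It adds that whether a parent is eligible "will be known by the providers prior to approaching a family".
- Section 7.2.1: a research-team member hands out the baseline survey to those who have consented.
- Section 16.5: a "training day for all providers who will implement the module and consent participants".

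Under section 5.1.1.2 a parent may refuse the surveys and stay in the parenting program. Section 8.3 leaves the model open, from t-tests to hierarchical regression, and does not mention baseline adjustment.

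**The concern.** In a site-randomised trial, randomisation balances the sites and the parents who attend them, apart from chance. It does not balance the parents who consent if consent is sought once the arm is fixed and under conditions that depend on the arm. Section 2.1 rests the causal claim on random allocation having removed systematic differences between the groups. That argument does not cover selection that happens after allocation.

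The primary outcome is self-reported knowledge, attitudes and behaviour on child sexual abuse (CSA) prevention, a topic that section 11.0 accepts may be uncomfortable. Willingness to answer such surveys could plausibly be related to that outcome. If willingness is drawn on differently in the two arms, part of the observed difference would reflect who agreed rather than what the module did.

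**Working it through.** **1. Order of events.** Sections 7.1 and 7.2.1 together give: site agrees to randomisation, experimental providers are trained, parents are approached, parents consent, T1 survey. Experimental providers know their arm by the time parents are approached. T1 comes before any intervention but covers consenters only, so it is already downstream of any selection.

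**2. Who recruits.**

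| Section | Recruits or takes consent |
|---|---|
| 4.1 | through providers, at sites already labelled by arm |
| 4.2, 7.2.1 | research team |
| 4.4 | providers, who know eligibility beforehand |
| 16.5 | providers who implement the module and take consent |

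Only experimental providers implement the module, so section 16.5 can be read as provider consent in one arm only. These statements cannot all describe one procedure.

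**3. Safeguards.** The documents contain no recruiter blind to arm, no common script, no log of parents approached and declining, and no baseline adjustment.

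**4. The plan's own figures, none disputed.** Effect size (8.2): (0.30 + 0.59)/2 = 0.445, stated as 0.45. Parents as Teachers and SafeCare, with 4 occasions and correlation 0.7 (borrowed from the Incredible Years paragraph): variance factor (1 + 3 × 0.7)/4 = 0.775; n = 2 × 0.775 × (1.960 + 0.842)²/0.45² = 60.1, so 61, and 62 with the noncentral F, as stated. Incredible Years: 8.0025 × (1.960 + 0.842)²/(10 × 3 × 0.45²) = 10.34, so 11 groups, as stated.

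**5. Size of bias, on assumptions only.** The documents give no consent rates and no link between consent and outcome.

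*Replacement model.* Bias = share of one arm replaced × difference of the replacements, here assumed 0.5 SD. Shares of 0, 10, 20 and 30% give 0, 0.05, 0.10 and 0.15 SD. Divided by 0.45: 0, 11, 22 and 33%.

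*Threshold model.* Parents consent when a standard normal trait exceeds a cut-off, and the trait correlates r with the outcome. With consent rate p, the mean trait among consenters is φ(z)/p, where z is the cut-off. Bias = r × the difference in these means.

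| Consent, one arm vs the other | Difference in means | Bias, r = 0.2 to 0.5 |
|---|---|---|
| 80% vs 80% | 0 | 0 |
| 80% vs 70% | 0.147 | 0.03 to 0.07 SD |
| 80% vs 60% | 0.294 | 0.06 to 0.15 SD (13 to 33% of 0.45) |
| 90% vs 60% | 0.449 | 0.09 to 0.22 SD |

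The sign reverses when the lower-consent arm is the other one.

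**6. False-positive rate with no true effect, unadjusted.** The rate is Φ(−1.960 − b/SE) + 1 − Φ(1.960 − b/SE), where b is the bias. SE = √(2 × 0.775/62) = 0.158 for Parents as Teachers and SafeCare. SE = √(8.0025/(14 × 10 × 3)) = 0.138 for Incredible Years. At 80% vs 60%, the 5% rate becomes about 7 to 15% and 7 to 19% respectively. At equal consent it stays at 5%.

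**7. Effect of adjusting for T1.** If the same shift b is present at T1 and later, and the T1 score correlates 0.7 with the later score, the adjusted comparison keeps b − 0.7b = 0.3b. For b from 0 to 0.15 that is 0 to 0.045 SD, or 0 to 10% of 0.45.

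**The case against.** The case for leaving the plan alone is substantial. Parents sign up for the parenting program independently before the research approach, are not told about randomisation, and lose nothing in the program by refusing. Both arms answer the same CSA assessment at T1, so the topic is not confined to one arm. There is also an ordinary reason for two scripts: only experimental parents complete the fidelity and satisfaction forms and may be asked to be recorded, and total assessment time is 60 minutes against 55.

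These points weaken the motive for differential consent and lower its likely size. They do not remove it. Not naming randomisation does not make the script or the recruiter the same in both arms, and the contradiction over who takes consent stands whatever the scripts say.

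A reader might go further and infer that the treatment script advertises a sexual-abuse module and so attracts or deters particular parents. The scripts are attachments that are not in the documents, so their content is unknown. A reader might also infer that consent is taken by providers in the experimental arm and by researchers in the control arm. Section 16.5 permits that reading but does not establish it.

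**Conclusion.** As written, the plan allows consent to depend on arm, and randomising sites cannot correct for that. This is a risk, not a demonstrated bias. The illustrative range is 0 to about 0.15 SD in either direction (0 to 33% of 0.45) without adjustment, and about 0 to 0.045 SD with T1 adjustment. The first range rests on assumed consent rates, replacement shares and correlations. It is not a bound: a 90% vs 60% split gives up to 0.22 SD. The second also needs a stable shift and the 0.7 autocorrelation, which section 8.2 states only for Incredible Years.

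It would be wrong to infer a minimum bias above zero, since equal consent in the threshold model gives none, or to infer that the bias must favour the module. The point justifies an inexpensive tightening of the plan; it does not show the design to be invalid.

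**What to change.** 1. Reconcile sections 4.1, 4.2, 4.4 and 16.5 so that the same recruiter role takes survey consent and runs T1 in both arms. State whether affiliates count as research team, because sections 9.1.2 and 9.1.4 let affiliate staff collect data alone.
2. In section 4.3, use the same core script wording in both arms up to completion of T1, and disclose the CSA content of the surveys. Give the experimental-only fidelity, satisfaction and recording information in a separate step after T1, subject to IRB agreement.
3. Log eligible, approached and consenting parents by site and arm, so that differential consent becomes visible.
4. In section 8.3, prespecify adjustment for the T1 Module Assessment in the primary comparison. The score is already collected.

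The cost is a script revision and an IRB amendment. The amendment must settle when experimental-only procedures are disclosed, since section 5.1.2 currently marks any alteration of consent as not applicable. A reader might suppose that no further resources are needed because section 4.2 already assigns the research team. That is not safe: consent for the 124 + 124 = 248 home-visiting parents takes place in their homes, so some travel or affiliate training may be needed. Sample sizes do not change. Recruiters may still know the arm, as the research team itself trains the experimental providers, so some risk remains.
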